2. STATISTICAL HYPOTHESES

The primary objective of this study is to compare the rate of effective hemostasis between and exanet and UC group. The following hypothesis will be evaluated:

Ho:
$$\pi_{UC} - \pi_{andexanet} = 0$$

HA: $\pi_{UC} - \pi_{andexanet} \neq 0$

where π is the rate of effective hemostasis in each group.

Comparison will be performed using a Cochran-Mantel-Haenszel (CMH) test stratified by time from symptom onset to the baseline imaging scan (< 180 minutes versus \geq 180 minutes). The difference in the proportion of participants with effective hemostasis between andexanet and UC group, the corresponding 95% confidence intervals (CIs) for the difference, and the p-value for the comparison will be provided.

The analysis of efficacy will employ an alpha spending function by Lan and DeMets based on Pocock boundaries. The primary efficacy objective of the study will be considered met if the proportion of participants with effective hemostasis in the andexanet group is statistically significantly higher than that in the UC group at interim (p < 0.0310) or in the final (p < 0.0277) analysis.

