3. SAMPLE SIZE DETERMINATION

Results (as of 30 Jun 2020) from the Phase 3b/4, single-arm, open-label Study ANNEXA-4 have shown that the rate of effective hemostasis is 79% (95% CI: 74% to 84%) based on evaluable participants with ICrH; the rate of effective hemostasis is 80% (95% CI of 75% to 84%) based on 340 efficacy-evaluable participants with all types of bleeding.

Based on these results, it is assumed that the rate of effective hemostasis in this study is 70% and 80% for participants treated with UC and andexanet, respectively. The 10% absolute difference represents a 33% risk reduction of not achieving effective hemostasis by andexanet as compared to UC, which is considered clinically meaningful. After accounting for early discontinuation rate and one interim analysis, it is estimated that a total sample size of approximately 900 participants (ie, 450 participants per group) will have approximately 90% power to detect a 10% absolute difference between andexanet and usual care in the rate of effective hemostasis at a 0.05 two-sided overall significance level.

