5.3.3. Sensitivity Analysis

The following sensitivity analysis will be performed to evaluate the robustness of the primary efficacy results:

Sensitivity analysis 1: The same analysis for the primary endpoint described in Section 5.3.2 with 2 stratified factors in the CMH test: intended PCC use (yes versus no) and the time from symptom onset to baseline imaging assessment (< 180 minutes versus \ge 180 minutes). For this analysis, participants who do not have intended PCC use data collected will be excluded.

Sensitivity analysis 2: The same analysis for the primary endpoint described in Section 5.3.2 on the PPS.

Sensitivity analysis 3: The same analysis for the primary endpoint described in Section 5.3.2 on the ITT Set, excluding participants with nonevaluable hemostatic status due to administrative reasons.

Sensitivity analysis 4: To evaluate the impact of the missing hemostatic status due to administrative reasons, 3 statistical methods for missing data imputation will be applied on the ITT Set as follows:

Page 20 of 52 Alexion Confidential **Worst-case scenario imputation**. In this case, missing hemostatic status in the andexanet group will be imputed as poor/none, whereas missing status in the UC group will be imputed as excellent/good. The same method used in the primary analysis described in Section 5.3.1 will be used to compare andexanet and UC. This imputation represents the worst possible case for missing hemostatic status; if the statistical comparison reaches significance (p < 0.05), the following imputation methods will not be performed.

Jump-to-control imputation. This approach imputes missing hemostatic status using only data from the UC group. For a given participant with missing status, his/her status will be generated based on the probability of effective hemostasis in the UC group estimated with available data, regardless of the treatment group this participant is randomized to.

Tipping point. In this case, missing hemostatic status will be imputed over a series of scenarios to evaluate at what point the significance in andexanet and UC comparison will be overturned.

A logistic regression model will be first estimated for the effective hemostasis, with treatment group and time from symptom onset to the baseline imaging scan in the model. Then, a shift parameter δ will be applied to the log odds ratio in the logistic regression model to impute the missing data.

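### The tipping-point analysis for missing hemostasis status uses one shift on the log odds ratio, so under ordinary coding it stops short of the worst case that triggers it and can show no tipping point although one exists

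*SAP*

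**What the plan says.** Sensitivity analysis 4 in SAP 5.3.3 deals with hemostasis status that is missing for administrative reasons, in three steps on the ITT Set.

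- **Worst case.** Here "missing hemostatic status in the andexanet group will be imputed as poor/none, whereas missing status in the UC group will be imputed as excellent/good". If this comparison still has p below 0.05, the other two methods are not run.
- **Jump-to-control.** Missing outcomes in both arms are drawn from the usual-care success probability.
- **Tipping point.** The aim is "to evaluate at what point the significance in andexanet and UC comparison will be overturned". A logistic model with treatment and the onset-to-scan stratum is fitted, and a shift δ "will be applied to the log odds ratio in the logistic regression model to impute the missing data". Each value of δ gets 100 imputed datasets, the stratified CMH test and Rubin's rule. The output is a plot of p against δ.

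The SAP does not say which arm δ acts on, how treatment is coded, what range δ covers, or which significance level defines loss of significance. In the primary analysis all nonevaluable cases count as poor/none in both arms (SAP 5.3.1, Table 3). Success is declared "at interim (p < 0.0310) or in the final (p < 0.0277) analysis" (SAP 2).

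**The concern.** The tipping point is reached only after one known scenario has removed significance at 0.05. A boundary therefore exists somewhere between the missing-at-random point and the worst case, and the analysis is there to find it. A path with one parameter finds it only if the path runs far enough in that direction.

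With reference coding (usual care as reference), shifting the log odds ratio changes the imputation probability for missing andexanet patients only. Missing usual-care patients are still imputed near their observed rate. As δ goes to minus infinity, the scenario becomes andexanet all failures with usual care at about 70%. The worst case puts usual care at 100%. If the boundary lies between these two points, the plot stays below the threshold for every δ. It would then look like complete robustness, although the worst case has already shown otherwise.

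**Working it through.** **Inputs from the documents.** Rates are "70% and 80% for participants treated with UC and andexanet, respectively" and size is "approximately 900 participants (ie, 450 participants per group" (both SAP 3). Final nominal level 0.0277, critical z = 2.2015; trigger level 0.05, critical z = 1.96.

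**Assumed.** The documents give no administrative missing rate. Let m be the fraction missing per arm, equal in both arms, with observed rates among the rest of exactly 80% and 70%.

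**Plan's own figure.** The SAP states "approximately 90% power to detect a 10% absolute difference between andexanet and usual care" "at a 0.05 two-sided overall significance level". At the final level alone: (0.10×√450 − 2.2015×√(2×0.75×0.25)) / √(0.21+0.16) = (2.1213 − 1.3481)/0.6083 = 1.271, a power of 89.8%. With both looks it is 91.2%. The stated power reproduces and does not depend on this point.

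**Step 1, worst case.** Difference = 0.8(1−m) − [0.7(1−m)+m] = 0.1 − 1.1m. At m = 0.04 (18 of 450):
- rates 0.768 and 0.712, difference 0.056
- SE = √[(0.768×0.232 + 0.712×0.288)/450] = 0.0292
- z = 1.92, p = 0.055, so the tipping point is run.

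**Step 2, adverse limit of δ with reference coding.** Difference = 0.8(1−m) − 0.7. The usual-care variance is 0.21/[450(1−m)], because its missing cases are imputed at the observed rate. At m = 0.04:
- difference 0.768 − 0.700 = 0.068
- SE = √[0.178176/450 + 0.21/432] = 0.0297
- z = 2.29, p = 0.022.

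No value of δ overturns the result at 0.05, 0.0310 or 0.0277.

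**Step 3, range of m affected.** Solving each expression for the critical z:

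| | z = 1.96 | z = 2.2015 |
|---|---|---|
| Worst case loses significance at m = | 3.89% | 3.27% |
| Extreme δ loses significance at m = | 5.15% | 4.31% |

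Because the trigger is set at 0.05, the tipping point is not run below m = 3.89%, whichever level is used to read the plot. The gap is therefore 3.9-5.2% judged at 0.05 and 3.9-4.3% judged at 0.0277. Since 0.0389×450 = 17.5 and 0.0431×450 = 19.4, the second range means 18 or 19 patients per arm.

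**Step 4, check with the planned method.** Two-stratum CMH with Rubin pooling:

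| Missing per arm | Worst case p | Extreme δ p |
|---|---|---|
| 18 | 0.056 | 0.022 |
| 20 | 0.081 | 0.031 |
| 22 | 0.115 | 0.042 |

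At 20 and 22 the plot still does not cross 0.05, but it does cross 0.0277 (at 22, near δ = −4).

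**Step 5, opposite shifts in the two arms, 22 missing per arm.** p rises from 0.0007 with no shift to 0.026 at ±2 on the logit, 0.09 at ±4, and 0.115 in the limit. That limit equals the worst case, so a crossing is always found once the worst case has lost significance.

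**Step 6, how often.** Simulated trials at 80% versus 70%, 450 per arm, with 2%, 3%, 5% and 8% missing per arm. Among trials significant on the primary analysis, the tipping point is triggered in about 12%, 26%, 60% and 92%. Of those triggered, the extreme δ never loses significance at 0.05 in 50%, 42%, 34% and 21%, and never at 0.0277 in 4%, 7%, 16% and 13%.

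**Other readings of δ.** If δ were added to the log odds of every missing patient, its adverse limit would be all missing cases failing in both arms. That is the primary analysis itself (p about 0.0014 at 18 per arm). The SAP names the log odds ratio, so this reading deserves less weight. A centred (±) treatment contrast would move the arms in opposite directions and would reach the worst case, but the SAP does not specify one.

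**The case against.** The strongest reply is that the missed scenarios are too extreme to matter. In the gap, all missing andexanet patients failing with usual care at its observed rate is still significant, so overturning requires something beyond that.

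- **At 0.05, 18 per arm:** every missing andexanet case must fail and about 97% of missing usual-care cases must succeed. If even 10% of the missing andexanet cases succeed, no usual-care rate overturns the result.
- **At 0.0277, 18 per arm:** with no missing andexanet successes, usual care must reach about 77-79%. With 20% andexanet successes it must be close to 100%. With 40% nothing overturns the result.

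These are administrative losses such as an unavailable scan or a transfer, for which near-opposite outcomes by arm are hard to credit. This stands. A reader might infer that modest, plausible departures (usual care a little better, andexanet a little worse) overturn the result unseen. The figures do not support that.

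A reader might also infer that δ cannot lower andexanet relative to usual care, or that no reading of the SAP reaches the worst case. Neither follows. Reference coding does lower andexanet; what it cannot do is raise missing usual-care outcomes. A centred contrast would do both. Shifting the experimental arm alone is also a legitimate one-parameter method.

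Finally, the worst-case p-value has already been obtained when the tipping point runs, so the loss of significance is not hidden. That is true, but it shows only that a boundary exists and does not locate it, which is the stated purpose. Jump-to-control does not help either, because it imputes both arms at the usual-care rate.

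**Conclusion.** The point holds as a limited design weakness in one sensitivity analysis. With ordinary reference coding the single shift ends short of the scenario that triggers the analysis, so the plot can show no tipping point when one exists. Under the planning rates with 450 per arm, this occurs at about 3.9-5.2% administratively missing per arm judged at 0.05, and at about 3.9-4.3% judged at the final level 0.0277.

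These ranges rest on equal missingness in the two arms, observed rates exactly at the planning values, and a missing rate that the documents do not give. Outside them the single-shift plot either is not run or does find a crossing. With sampling variation the ranges blur, as the simulated frequencies show. The primary test, error control and power are untouched. Severity is low: worth changing because it costs little.

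**What to change.** Replace the single δ by two shifts on the log odds, one for missing andexanet outcomes and one for missing usual-care outcomes. Run them over a two-way grid from no shift in either arm (missing at random) to the worst-case corner (andexanet strongly negative, usual care strongly positive). Keep the 100 imputations per grid point, the stratified CMH test and Rubin's rule.

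Report the boundary where significance is lost at the trial's own level, 0.0310 if the study stops at the interim and 0.0277 at the final analysis. State the treatment coding and the range of each shift, so that readers can judge the plausibility of the boundary. The one-arm path remains visible as one edge of the grid.

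While editing, the trigger should be looked at too. It uses 0.05, so a worst-case p between the trial's level and 0.05 cancels the tipping point although significance at the trial's level is already lost.

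The cost is a few sentences in the SAP, slightly more programming, and a two-way display instead of a line plot. No new data are needed.

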5.4. Secondary Endpoint Analysis

The secondary objective of this study is to evaluate the effect of and examet versus UC on anti-fXa activity. The secondary endpoint is the percent change in anti-fXa activity from baseline to nadir during the first 2 hours post-randomization.

Analyses for anti-fXa activity will be based on the ITT Set. Change and percent change from baseline at each scheduled time point and from baseline to nadir 2 hours post-randomization will be summarized by treatment group. Baseline is defined as the last assessment prior to randomization.

And exanet and UC will be compared by ANCOVA on the ranked percent change from baseline to nadir 2 hours post-randomization, adjusted for covariates of time from symptom onset to the baseline imaging scan (< 180 minutes versus \geq 180 minutes) and baseline anti-fXa activity. Missing data for this analysis will be handled as follows:

Section 6.1 details the handling of missing baseline data and data above and below the upper and lower limit of quantitation.

Participants with missing baseline value will be excluded from the analysis. Remaining missing data at 1 and 2 hours post-randomization will be imputed using the multiple imputation method described by Rubin (1967). Covariates included in the imputation model include treatment group, time, time-by-treatment interaction, and baseline anti-fXa activity. Based on the imputed datasets, nadir value and percent change from baseline to nadir will be derived. ANCOVA on the ranked percent change to nadir will be used to generate the p-value for comparing andexanet and UC. This imputation process will be run 100 times, and 100 p-values will be generated; the median p-value rule, as outlined in Eekhout et al (2017), will be applied to derive the final p-value.

Figures displaying the line plots of anti-fXa activity by treatment group at baseline and at 1 and 2 hours post-randomization and boxplots at baseline and nadir by treatment group will be presented overall and for each prior FXa inhibitor.

5.5. Additional Endpoint Analysis

The tertiary efficacy endpoints are listed in Section 1.1. All tertiary efficacy analyses will be performed on the ITT Set. No missing data will be imputed.

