10.5.4.4. Additional Efficacy Analyses

Thrombin generation parameters (with ETP as the primary measure) will be obtained at baseline, 1 hour, and 12 hours post-randomization. The difference between the two treatment groups will be evaluated using a mixed effects model similar to the model described below for the analysis of the NIHSS and GCS scores.

The change from baseline in NIHSS and change from baseline in GCS will be analyzed using a mixed linear model with covariates, including the baseline measurement and the following fixed effect terms:

- Stratification factor of time from symptom onset to baseline imaging scan (< 180 minutes vs. ≥ 180 minutes)
- Treatment arm (usual care/andexanet)
- Time (measurements at 2, 3, 6, 12, 24, and 72 hours post-randomization)
- Treatment-by-time interaction

Patients will be treated as a random effect to take account of the correlation of the measurements within the same patient.

Neurologic deterioration at 24 hours defines deterioration as meeting at least one of the following 2 criteria:

- An increase in NIHSS score ≥ 4 at 24 hours post-randomization compared with baseline;
- A decrease in GCS score ≥ 2 at 24 hours post-randomization compared with baseline.

The CMH test stratified by time from symptom onset to baseline imaging scan will be used to test the treatment difference in the proportion of neurologic deterioration at 24 hours.

Change from baseline in mRS scores at 30 days post-randomization will be analyzed using a proportional odds model adjusted for baseline mRS, the stratification factor, treatment arm, and potentially other clinical factors.

The relationship between anti-fXa activity and the achievement of clinical events such as hemostatic efficacy and mortality will be evaluated. A logistic regression adjusted for potentially other clinical factors, the stratification factor in the primary efficacy analysis, and treatment arm will be used to evaluate the relationship.

Further details of these analyses will be provided in the SAP.

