A preplanned sample size re-estimation (SSR) will be performed by the DSMB-associated statistician to reassess the required size of the study population based on estimation of the primary endpoint at the interim analysis. If an increase is required, the total number of participants enrolled may be increased to 1200 participants (with an addition of 300 participants).

Statistical Analysis Plan ALXN2070 18-513 (Amendment 3)

There are 2 data cutoff (DCO) points in ANNEXA-I. The first DCO is for the planned interim analysis of the primary efficacy endpoint by the DSMB, after 50% of the anticipated patients have been adjudicated for effective hemostasis. If the DSMB recommend stopping the study based on the interim analysis results, the first DCO will be used for confirmatory analyses of efficacy endpoints (primary efficacy population, N = 450). Enrollment of patients will be continued without interruption from the first DCO until the stop decision is communicated; then recruitment will be closed which is the second DCO. The second DCO captures the data from all patients who participate in the study (extended population, N = 450 + X) and forms the basis for the safety analyses along with sensitivity analyses of the efficacy endpoints.

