5. STATISTICAL ANALYSIS

5.1. General Considerations

During the conduct of the study, the Sponsor and Investigators will be blinded to the aggregated efficacy and safety summaries. In addition, all unblinded analyses that are required to support the DSMB will be performed by an independent unblinded DSMB statistician. These analyses will be performed under the direction of the DSMB according to the analyses described the DSMB Charter. The results of these unblinded analyses will not be available to the Sponsor or Investigators until after database lock.

The safety interim analyses will follow the same procedures as the efficacy interim analysis (see Protocol Section 10.7), with the Sponsor remaining blinded to the results of these analyses unless the DSMB recommends stopping the study early.

Once the study is complete and the final database lock is performed, the study will be fully unblinded and the final analyses will be performed.

All efficacy and safety endpoint parameters will be summarized descriptively.

For continuous variables, the number of observations, mean, median, SD, first quartile, third quartile, interquartile range, and minimum and maximum values will be presented. For categorical variables, unless specified otherwise, counts and percentages will be based on the number of participants with nonmissing values in each treatment group and total. Inferential statistics will be presented only when specified.

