5.5.2. Neurologic Deterioration at 12 and 24 Hours

The proportion of participants with neurologic deterioration at 12 hours, defined as the number of participants with a \geq 7-point increase from baseline to 12 hours in NIHSS, will be tabulated. Neurologic deterioration at 24 hours is deteriorations meeting at least 1 of the following 2 criteria.

- An increase in the NIHSS score \geq 4 at 24 hours post-randomization compared with baseline.
- A decrease in the Glasgow Coma Scale (GCS) score ≥ 2 at 24 hours post-randomization compared with baseline.

A CMH test stratified by time from symptom onset to the baseline imaging scan will be used to compare and exanet and UC in the proportion of neurologic deterioration at 12 and at 24 hours post-randomization, respectively. The difference in the proportion and its 95% CI will be reported.

By-participant listings of neurologic deterioration at 12 and 24 hours will be provided.

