5.7.2.5. Deaths

The number and percentage of participants with AEs leading to death will be presented by SOC and PT as described above.

All deaths will be assessed by the EAC blinded to treatment group. Deaths occurring up to 30 days post-randomization will be referred below as 30-day death or 30-day mortality. Bleeding mortality is defined as deaths occurring within 72 hours post-randomization not associated with TEs.

All 30-day deaths, 30-day death occurring during index hospitalization, and bleeding-related mortality (defined as any death within 72 hours from randomization and not associated to the occurrence of an identified TE) will be summarized by treatment group and total based on the following causes:

- All causes
- Cardiovascular (CV) causes (resulting from myocardial infarction, sudden cardiac death, heart failure, stroke, cerebral vascular procedures, CV hemorrhage, or other)
- Non-CV causes (resulting from non-CV hemorrhage and non-CV procedure or surgery)

Time to death by all causes up to 30 days post-randomization will be analyzed using a Cox proportional hazards model adjusted for time from symptom onset to the baseline imaging scan (< 180 minutes versus \geq 180 minutes) and treatment group. Participants who did not die or discontinued prior to Day 30 will be censored at the day of the last assessment.

Page 28 of 52 Alexion Confidential Kaplan-Meier method will be used to analyze time to death with the same censoring rule. Participants who completed the study (ie, Day 30) will be censored at the day of the last assessment. Probabilities of 30-day death at different time points and median time to death will be presented by treatment group.

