The majority of cases will not require review by adjudicators as the outcome rating will be obvious based on the core laboratory interpretation, NIHSS scores, and lack of additional treatments or procedures. An algorithm will be applied to the data from the imaging core laboratory and information provided by the sites on CRFs. The algorithm will determine if the case can be immediately classified as excellent, good, or poor/none or whether the case requires review by adjudicators and additional review by the EAC. Cases will be referred for EAC review, if the change in hematoma volume is < 35% and the change in the NIHSS score between baseline and 12 hours is < 7 and if one of the following criteria is met:

- baseline or 12-hour scans (11 to 15 hours post-randomization) missing, uninterpretable, or fall outside the collection window.
- NIHSS scores missing or fall outside the collection window for either baseline or 12-hour evaluations.
- Cases where the blinded imaging core laboratory readers indicate that review by the EAC is needed (or 3 readers disagree on classification of hematoma volume change).
- Cases where the participant was either sedated or intubated for either baseline or 12-hour NIHSS assessment (or both).
- Documented procedures that could potentially drain hematoma between 3- and 12hours post-randomization.
- Cases, where it is determined that there is insufficient information or where it is not otherwise possible to properly assess the effect of treatment, will be further classified by the EAC as follows:
 - Nonevaluable due to administrative reasons (eg, follow-up scans not available/performed/interpretable and the participant transferred to another

facility for administrative purposes); these participants will be analyzed as having poor/none effective hemostasis.

• Nonevaluable due to clinical reasons (eg, the participant died and the participant had unplanned surgery draining hematoma); these participants will be analyzed as having poor/none effective hemostasis.

Identifying Rescue Medications/Procedures

Rescue medications are identified from the concomitant medication CRF pages based on the following:

- 1. If indication for medication is "TO ACHIEVE HEMOSTASIS FOR CONTINUOUS (WORSENING) INTRACEREBRAL HEMORRHAGE BLEED," "TO ACHIEVE HEMOSTASIS FOR INITIAL BLEED," or "TO ACHIEVE HEMOSTASIS FOR NEW BLEED RE-BLEED" (except for tranexamic acid, which is permitted regardless of indication).

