On treatment nadir is the minimum anti-fXa activity post-randomization (ie, value observed at either 1- or 2-hour post-randomization evaluation). A percent reduction will be calculated as the ratio between the maximum reduction from baseline and the baseline value, multiplied by 100.

Length of Hospitalization and Rehospitalization

The following steps will be followed to calculate the length of hospitalization (or rehospitalization):

- The length of stay (LOS) will be calculated as discharge date/time admission date/time + 1.
- If the participant admission time and the discharge time are missing and the dates are the same, the LOS will be assumed to be 1 day.
- If the participant admission time and the discharge time are missing and the dates are not the same, the LOS will be calculated using the date portion of the dates plus 1.
- If the discharge date is missing and there is no new admission date, the date of the 30-day visit or the date of death (whichever is earlier) will be imputed as the discharge date.
- If the participant has withdrawn consent, the discharge date will be imputed as the date of the 30-day visit or the date of death (whichever is earlier and/or available).

Neurologic Deterioration at 24 hours

Neurologic deterioration at 24 hours is defined as an NIHSS increase \geq 4 at 24 hours compared to baseline or a GCS score decrease \geq 2 at 24 hours compared to baseline.

Neurologic Deterioration at 12 hours

Neurologic deterioration at 12 hours is defined as an increase of \geq 7 point from baseline to 12 hours in NIHSS.

Utility-Weighted mRS

Mean utility values will be based on EQ-5D-5L at the same visit and will be determined by averaging the utilities of all participants within each mRS category.

AEs With Partial or Missing Start and End Date

If the start date of an AE is partially or completely missing and the end (stop) date and time of the AE do not indicate that it occurred prior to the first dose, then the determination of treatmentemergent status will be based on the following:

- If the start year is after the year of the first dose, then the AE is treatment emergent.
- If the start year is the same as the year of the first dose and:
 - If the start month is missing, then the AE is treatment emergent.
 - If the start month is present and is the same as or after the month of the first dose, then the AE is treatment emergent.

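### SAP 5.5.2 gives no rule for death before the 12- or 24-hour neurologic score, so the deterioration comparison most naturally becomes conditional on survival

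*SAP*

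**What the plan says.** SAP 5.5.2 and the derived-variable definitions in SAP 6.1 set two deterioration endpoints.

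- At 12 hours: "Neurologic deterioration at 12 hours is defined as an increase of" 7 or more NIHSS points from baseline.
- At 24 hours: "Neurologic deterioration at 24 hours is deteriorations meeting at least 1 of the following 2 criteria", namely an NIHSS rise of 4 or more, or a GCS fall of 2 or more.

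Protocol 10.5.4.4 uses the same score-only construction at 24 hours ("Neurologic deterioration at 24 hours defines deterioration as meeting at least one of the following 2 criteria"), and Protocol 10.5.3.3 lists the 12-hour NIHSS endpoint. SAP 5.5.2 compares each proportion with a CMH test stratified by onset-to-scan time and reports the difference with its 95% CI. None of these places mentions death.

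Two general rules then apply. SAP 5.5 says: "All tertiary efficacy analyses will be performed on the ITT Set. No missing data will be imputed". SAP 5.1 says of categorical variables, unless something else is specified: "counts and percentages will be based on the number of participants with nonmissing values in each treatment group and total".

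Elsewhere the SAP does give death an outcome. In the primary endpoint, the class "Nonevaluable due to clinical reasons (eg, the participant died and the participant had unplanned surgery draining hematoma") is analysed as poor/none. In SAP 5.5.3, death is mRS 6 and falls in the unfavourable category. In SAP 6.3.2 it receives utility 0.

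**The concern.** A patient who dies before the assessment has no 12- or 24-hour score. Under the rules above, that patient most naturally drops out of both numerator and denominator, although the analysis is labelled ITT. Survival to the assessment may itself depend on treatment. If early deaths differ between arms, the comparison leaves out the patients with the worst course and does not show that part of the difference.

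The plan is also uneven. An NIHSS rise of 7 or more at 12 hours is a component of the primary endpoint. The same early death can therefore be a failure in the primary analysis and absent from the separate analysis of that component. Early deaths are foreseeable: Protocol 1.0 cites 30-day mortality above 30-40% in intracranial hemorrhage, and SAP 5.7.2.5 defines a 72-hour bleeding mortality. What is at stake is the meaning of one set of additional endpoints, not the success criterion of the trial.

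**Working it through.** **Plan's own figure.** The documents state no power or precision for this endpoint. The only power figure, about 90% for the primary endpoint, reproduces (89.8% as a single test at 0.0277 with 450 per arm and 70% versus 80%) but does not bear on this point.

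**Inputs from the documents.** 450 per arm (SAP 3). If the trial stops at the interim, "the first DCO will be used for confirmatory analyses of efficacy endpoints (primary efficacy population, N = 450") applies, which is 225 per arm at 1:1 allocation.

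**Assumed inputs.** Deaths before the assessment, d0 (usual care) and d1 (andexanet). Deterioration among survivors q, taken as equal in both arms: 0.20 at 24 hours and 0.10 at 12 hours.

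**Formulas** (usual care minus andexanet; positive favours andexanet).

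- Survivors only: q − q = 0, whatever the death rates.
- Death as deterioration: p = d + (1 − d)q in each arm, so p0 − p1 = (d0 − d1)(1 − q). This is the omitted difference.
- Full ITT denominator with death as a non-event: (1 − d0)q − (1 − d1)q = −(d0 − d1)q.
- SE = √[p0(1 − p0)/n + p1(1 − p1)/n].

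**One case in full**, d0 = 0.03, d1 = 0.02, q = 0.20: p0 = 0.03 + 0.97 × 0.20 = 0.224; p1 = 0.02 + 0.98 × 0.20 = 0.216; difference 0.008. SE at n = 450 is √[(0.1738 + 0.1693)/450] = 0.0276, so the ratio is 0.29.

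| Time, q | Deaths, usual care vs andexanet | Omitted difference (points) | In SE, 450 per arm | In SE, 225 per arm |
|---|---|---|---|---|
| 24 h, 0.20 | 1% vs 0.67% | 0.27 | 0.10 | 0.07 |
| 24 h, 0.20 | 3% vs 2% | 0.8 | 0.29 | 0.20 |
| 24 h, 0.20 | 5% vs 3% | 1.6 | 0.57 | 0.40 |
| 24 h, 0.20 | 8% vs 4% | 3.2 | 1.11 | 0.79 |
| 24 h, 0.20 | 10% vs 5% | 4.0 | 1.37 | 0.97 |
| 24 h, 0.20 | 5% vs 5% | 0 | 0 | 0 |
| 24 h, 0.20 | 2% vs 3% | −0.8 | −0.29 | −0.20 |
| 12 h, 0.10 | 1% vs 0.5% | 0.45 | 0.22 | 0.15 |
| 12 h, 0.10 | 3% vs 2% | 0.9 | 0.41 | 0.29 |

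**The other reading.** At 8% versus 4% deaths, a full ITT denominator gives 0.92 × 0.20 − 0.96 × 0.20 = −0.8 points, against the arm with fewer deaths.

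**Example in counts** (assumed, 450 per arm, 24 h; unstratified, Wald CI). There are 27 deaths on usual care and 9 on andexanet; 85 of 423 and 88 of 441 survivors deteriorate.

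- Deaths left out: 20.1% vs 20.0%, difference 0.1 points (95% CI −5.2 to 5.5).
- Death as deterioration: 112/450 vs 97/450, 24.9% vs 21.6%, 3.3 points (−2.2 to 8.8).
- Full denominator, death as non-event: 18.9% vs 19.6%, −0.7 points (−5.8 to 4.5).

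**The case against.** *The exclusion is not written down.* This stands. SAP 5.5.2 does not speak of deaths or denominators. The rule in SAP 5.1 is a general one for summary counts and yields to anything specified otherwise, and SAP 5.5 names the ITT Set. A reader might infer that SAP 5.5.2 expressly removes deaths. It does not; removal follows only from reading 5.1, 5.5 and the score-only definitions together. The alternative reading does not rescue the plan, because it scores death as no deterioration.

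*The size is assumed.* This also stands. Protocol 4.1 and 4.2 limit entry to NIHSS 35 or less and hematoma volume 60 mL or less and exclude GCS below 7 (with an exception for non-neurologic intubation or sedation). That makes the upper rows of the table less plausible.

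*Little depends on it.* Largely true. The endpoints are outside the hierarchy in SAP 5.1.1. SAP 5.7.2.5 reports 72-hour deaths not associated with a thrombotic event and adds: "Probabilities of 30-day death at different time points and median time to death will be presented by treatment group". An early survival imbalance would be visible there. Separate death tables do not, however, change what this CMH difference and its CI estimate.

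*The protocol prespecifies score change, so adding death is a preference.* Partly right: a supplementary analysis would also expose the problem. The SAP's own treatment of death in the primary endpoint, mRS and utilities favours making it the main analysis, provided the protocol definition stays visible.

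**Conclusion.** The concern holds as a missing rule whose most natural consequence is a survivor-conditional comparison. Its size cannot be computed from the documents. With equal deterioration among survivors it is negligible at low early mortality, about 0.3 SE at 3% versus 2% deaths, and 1.1 SE at 8% versus 4% (24 hours, q = 0.20, 450 per arm). Only the two most unequal rows exceed 1 SE, and none reaches conventional significance on its own.

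Two stronger inferences are not supported. A reader might infer that the gap favours one treatment; its direction follows whichever arm has more early deaths, and nothing in the documents says which that will be. A reader might also infer that the trial's main conclusions are at risk; the primary endpoint already counts a death that prevents the 12-hour evaluation as poor/none, and the secondary endpoint is anti-fXa activity.

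**What to change.** Before unblinding, amend SAP 5.5.2 and 6.1 as follows.

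1. Count death before the 12- or 24-hour assessment as deterioration at that time point, in line with the primary endpoint.
2. Keep survivors without the needed scores as missing, report their number by arm, and do not code them as non-events. If 8% versus 4% of survivors were unscored (assumed, q = 0.20), such coding alone would shift the difference by (0.92 − 0.96) × 0.20 = −0.8 points.
3. At 24 hours, state one rule for survivors with only NIHSS or only GCS that applies whether or not the available score meets its criterion. Either classify on the available score in both directions, or require both scores. Otherwise a single score that meets its criterion makes the patient an event, while one that does not leaves the patient unclassified, so such patients can enter only as events.
4. Report the protocol's score-only analysis as a sensitivity analysis, and list the change in SAP 6.5, which at present records only the enrolled-set definition.

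The cost is wording in three sections and minor programming; survival status is already scheduled in Protocol Appendix A. The downside is that the endpoint becomes deterioration or death from any cause, which departs from the protocol's score-only definition. The sensitivity analysis keeps that definition in view.
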